- ECG: subjects who have a QTcF > 500 ms at the Month 6 assessment or increase > 60 ms from the highest value prior to the first dose in the main study

2. **Per Protocol Extension Analysis Set (PP EAS)**: All subjects from Treatment Extension Analysis Set, excluding those identified as having major protocol deviations that could potentially affect the efficacy assessments up to Month 12. Subjects will be analyzed according to randomized treatment.

3. **Follow-up Extension Analysis Set (FU EAS)**: All subjects from the main study who entered the extension study and received at least one dose of study drug with the exception of subjects whose Month 6 assessment subsequently met any of the discontinuation criteria, and who entered the Post-Treatment Follow-Up Period. Subjects will be analyzed according to randomized treatment.

4. **Extension Safety Analysis Set (ESAF)**: All subjects randomized into the extension study who received at least one dose of study drug irrespective of the treatment received. Subjects will be analyzed according to treatment received.

5. **Follow Up Safety Analysis Set (FU SAF)**: All subjects randomized into the extension study who received at least one dose of study drug irrespective of the treatment received, and who entered the Post-Treatment Follow-Up Period. Subjects will be analyzed according to treatment received.

6. **Extension Pharmacokinetic (PK) Set**: all subjects who were randomized and received active study medication in the main study, had no major protocol deviations impacting PK throughout the main study or extension and with available PK data. Subjects will be analyzed according to treatment received.

7. **Extension Pharmacodynamic (PD) Set**: all subjects who were randomized and received active study medication in the main study, had no major protocol deviations impacting PD throughout the main study or extension and with available PD data. Subjects will be analyzed according to treatment received.

In general, analyses of efficacy will be conducted using the TEAS, PP EAS (when specified) and FU EAS sets, analyses of safety will be conducted using the ESAF and FU SAF, and analyses of PK and PD will be conducted using the PK and PD Sets accordingly.

The actual treatment will be derived as follows, based on daily e-diary IMP intake data:

Treatment kits will be dispensed to the subjects as follows:

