- on Month 6 and Month 9 visits, subject will receive two kits, one for linzagolix/placebo (monthly kit) and one for the ABT/ABT placebo (3-monthly kit).

- On Month 7, Month 8, Month 10 and Month 11 visits, subject will receive one kit only, for linzagolix/placebo. The number of days with one pink tablet, one grey tablet and one red capsule taken based on e-diary IMP intake data for each treatment will be computed. Data from "Today" will be used primarily. If data from today is missing, data from "Yesterday" of the

following day will be considered. If the e-diary is not completed for a day (neither "Today" nor "Yesterday" of following day), it will be assumed that no intake of drug was taken on that day.

Further rules are as follows:

- Treatment administration errors:
 - If a subject received placebo with placebo ABT on more than 50% of days (even if it is not planned), then the actual treatment group will be placebo with placebo ABT for the extension period.
 - Otherwise, the active treatment (combined with add-back or placebo add-back) with the most days taken will be assigned for the extension period.
 - If the number of days is equal for two treatments groups containing active treatment, then LGX 200 mg with ABT will be assigned for the extension period.
- If a subject discontinued, only data received up to discontinuation will be used.

All analyses for the extension study will be described according to the combined treatment group based on the treatment on the main study and the extension study.

For the combined actual treatment groups, the actual treatment during the main study and the actual treatment during the extension study comprise the following four combined actual treatment groups. It is possible that the derived actual treatment group will not correspond to any of the combined planned treatment groups; thus the combined actual treatment group will be derived as follows:

Actual treatment Main study	Actual treatment Extension study	Combined actual treatment group
Combination planned in the pr	otocol	
Placebo	LGX 75 mg	Placebo / LGX 75 mg
Placebo	LGX 200 mg + ABT	Placebo / LGX 200 mg + ABT
LGX 75 mg	LGX 75 mg	LGX 75 mg
LGX 200 mg + ABT	LGX 200 mg + ABT	LGX 200 mg + ABT
Combination not planned in the protocol (but possible with treatment administration errors)		
Placebo	Placebo	Placebo / LGX 75 mg
LGX 75 mg	Placebo	LGX 75 mg

LGX 200 mg + ABT	Placebo	LGX 200 mg + ABT
LGX 75 mg	LGX 200 mg + ABT	LGX 75 mg

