Due to a system error in Signant Health device, some subjects from non-US sites wrongly completed diaries in the Extension study in English language instead of a specific language. Data with English language (when evaluation is done by subject, i.e. QSEVAL=SUBJECT) for such subjects should not be considered in analysis.

Handling of duplicate records

- A change of eDiary device vendor (vendor to Signant Health vendor) occurred during the study.
- Some subjects may have entered data in the two different devices during the transition period. In case of duplicates results on the same day for daily diaries or on the same visit for monthly questionnaires, data from the new vendor (Signant Health) will be used for analysis.
- In case of duplicates within the same device (same date, same name), the first non-empty record (with earliest date/time) should be used for analysis.

Daily Records entered after 00:00

For daily diaries, records entered with a time between 00:00 (midnight) and 02:00 AM should be considered for the previous day.

Additional rules to specific eDiary domains:

Analgesic use data:

- Analgesic use data from "Today" will be used primarily. If data from "Today" is missing, data from "Yesterday" of the following day will be considered

IMP Intake Data:

- IMP Intake data from "Today" will be used primarily. If data from "Today" is missing, data from "Yesterday" of the following day will be considered

device specific rules

NOTE: by design, when a subject is completing a questionnaire (daily or monthly) on a device, the device automatically saves all answers provided by the subject as soon as

CRS-BS-TP-000005 V 2.0

Page 35 of 99

recorded, unless the subject uses the "previous" button to come back to already answered question(s) within the questionnaire and changes her answer(s) prior to finishing the questionnaire.

There are several triggering questions in the study questionnaires: the next question(s) presented to the subject will depend on the answer chosen by the subject to the current question.

Due to device design issue, when an answer to a triggering question has been changed by the subject (using previous button), the device keeps subsequent answer(s) to the previously triggered question(s), even if this/these question(s) is/are no longer relevant considering the new answer to the triggering question.

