9.5. Appendix E: Mapping rules for ediary data

Table 5 Mapping Rules for Kayentis Device

	cut off date (from eCRF)	First IMP intake in EXT	First IMP intake in EXT
	Cytel mapping	from MAIN TREAT to EXT TREAT	from MAIN FU to EXT TREAT
	Cytel action on Menstrual data	n/a	n/a
	Cytel action on IMP intake data	mapping	n/a - missing in final DB
	impact on data	data present in the Main datasets should be considere d for the analysis of the extension study	data present in the Main datasets should be
•	Schedul e of Kayenti s daily diary	remaine d in MAIN TREAT MENT (due to Covid remote visit or to site error in diary completi on)	resched uled to MAIN FU (due to site
	Patient status	patient was included in EXT	patient was included in EXT
	impacte d visit	Month 6	Month 6
	Cas e #	~	N

Kissei / Cytel Confidential: This is a controlled document and shall not be changed, saved, copied or reproduced by any unauthorized person.

Page **87** of **99**

Cytel CONFIDENTIAL - Kissei

SAP version: 3.0, Date: 28-AUG-2023

	MONTH 6 visit date	MONTH 12 visit date
	from EXT TREAT to MAIN FU	n/a - remain in MAIN Extension DB
	n/a	n/a
	"Is the subject eligible to the 6 months treatment free follow-up?" is YES> delete answers to YIMPI and IMPI	delete answers to YIMPI and IMPI
considere d for the analysis of the extension study	data present in the Extension datasets should be considere d for the analysis of the Main study	Data regarding IMP intake will be present for this period
error in diary completi on)	resched uled to EXT TREAT MENT (site error in diary completi on)	remaine d in Extensio n TREAT MENT (due to Covid remote visit or
	patient entered MAIN FU	patient entered Extensio n FU
	Month 6	Month 12
	m	

Kissei / Cytel Confidential: This is a controlled document and shall not be changed, saved, copied or reproduced by any unauthorized person.

Page 88 of 99

		First IMP intake in MAIN
	- Kayentis cleaning needed	n/a - remain in MAIN DB
		delete the answers to "is it your Menstrual period?" and start date questions, if any
	CASE by CASE review	n/a - missing in final DB
	duplicates data will be present across the datasets	Data regarding IMP intake will not be present for this period and data regarding menstrual
to site error in diary completi on)	patient entered diary data in both Main Main Extensio n studies each day	remaine d in SCREE NING (due to site error in diary completi on)
	whateve r status: DUPLIC ATE ENTRIE S	patient entered MAIN TREAT MENT
	Month 6	Day 1
	ى ك	ω

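### SAP 4.1 has no rule for a subject with no countable eDiary intake day, and its tie rule, read literally, files such a placebo-to-75 mg switcher under 200 mg + ABT

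*SAP*

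**What the plan says.** SAP 4.1 sets the data source: "The actual treatment will be derived as follows, based on daily e-diary IMP intake data". The unit of counting is "The number of days with one pink tablet, one grey tablet and one red capsule taken based on e-diary IMP intake data for each treatment". The same-day entry is used first, then the next day's entry for the day before. If neither exists, "it will be assumed that no intake of drug was taken on that day".

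Three assignment rules follow, under a bullet on treatment administration errors:

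1. Placebo, if placebo with placebo ABT was taken on more than half of the days.
2. "Otherwise, the active treatment (combined with add-back or placebo add-back) with the most days taken will be assigned for the extension period".
3. "If the number of days is equal for two treatments groups containing active treatment, then LGX 200 mg with ABT will be assigned".

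A table then combines main-study and extension treatment into four groups. The Extension Safety set (ESAF) and the Follow-up Safety set (FU SAF) are analysed by treatment received. The three efficacy sets are analysed by randomized treatment. ESAF entry needs one dose of study drug, not a diary record of it.

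The SAP also describes intake data being lost or set aside. In Appendix E, Table 5, Case 2 (an extension subject whose diary was wrongly rescheduled to main-study follow-up), the entry for IMP intake is "n/a - missing in final DB". SAP 6.2.6.3 says that subject-entered diaries completed in English at non-US sites, through a fault in one device, "for such subjects should not be considered in analysis".

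**The concern.** The three rules are the only assignment algorithm in the SAP. They cover placebo-majority, active-majority and equal counts. They do not separately cover a subject for whom nothing can be counted, and nothing limits the equal-count rule to counts above zero. A programmer must either apply the tie rule to 0 versus 0 or make up a rule.

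If the tie rule is applied, the error runs one way. Safety data from a woman who was given 75 mg without add-back are reported as 200 mg with add-back. These are the two regimens whose bone, hypoestrogenic and bleeding profiles the extension is meant to describe separately. The women most likely to have no countable day are those with very short extension treatment. Some of them may have stopped for an adverse event, so the label matters more than the head count suggests.

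**Working it through.** **Step 1. Apply the rules to zero days.** Let the countable days be 0 on 75 mg, 0 on 200 mg + ABT and 0 on placebo.

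- Rule 1 is not met: 0 is not more than 50% of the days.
- Rule 2 has no winner: 0 versus 0.
- Rule 3 applies because the counts are equal, so the derived extension treatment is LGX 200 mg + ABT.

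**Step 2. Pass that result through the combined-group table.**

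| Main-study treatment | Regimen given in extension | Derived, 0 days | Combined group | Right? |
|---|---|---|---|---|
| Placebo | 75 mg | 200 mg + ABT | Placebo / LGX 200 mg + ABT | No |
| Placebo | 200 mg + ABT | 200 mg + ABT | Placebo / LGX 200 mg + ABT | Yes, by default |
| 75 mg | 75 mg | 200 mg + ABT | LGX 75 mg | Yes, the table overrides |
| 200 mg + ABT | 200 mg + ABT | 200 mg + ABT | LGX 200 mg + ABT | Yes |

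Only the placebo-to-75 mg switcher is misfiled. A single countable 75 mg day is enough to prevent it: 1 versus 0 gives Placebo / LGX 75 mg.

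**Step 3. Can such a woman be in the safety set?** Yes. The first extension dose is taken at the site and its time is recorded in the eCRF (Protocol 10.2.1.1), so ESAF entry does not depend on the diary.

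**Step 4. Which outputs move?** ESAF tables by group, and FU SAF tables (including time to first menses) if she entered follow-up. The efficacy sets use randomized treatment. The PK and PD sets require active medication in the main study, so they contain no main-study placebo subjects.

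**Step 5. Size.** The plan's own figure reproduces: 450 × 0.80 = 360, and 360 × 0.80 = 288 entrants (SAP 2.2). Assume equal retention across the three main-study arms, which the documents do not state. With 1:1 allocation of placebo subjects (SAP 2.3):

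- placebo switchers: 288 / 3 = 96
- each switch group: 96 / 2 = 48

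| Women misfiled | Group sizes 75 mg / 200 mg + ABT | Share of 75 mg switchers lost | Share of 200 mg + ABT group wrong |
|---|---|---|---|
| 1 | 47 / 49 | 1/48 = 2.1% | 1/49 = 2.0% |
| 2 | 46 / 50 | 2/48 = 4.2% | 2/50 = 4.0% |
| 5 | 43 / 53 | 5/48 = 10.4% | 5/53 = 9.4% |

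The documents give no count of affected women. The rows show a scale, not an estimate.

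**The case against.** **The tie rule was meant for something else.** It sits under treatment administration errors and was probably written for a woman who took two active regimens for equal numbers of days. That is a fair reading of intent. But the text does not say so, and no other rule covers zero days.

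**Kits must already be used.** A reader might infer that the SAP ignores the kits altogether. It cannot. In the double-dummy design both regimens consist of one pink tablet, one grey tablet and one red capsule (Protocol 11.2 and 11.3), so the diary alone cannot tell them apart. Counting days for each treatment requires kit contents, and SAP 4.1 sets out the dispensing schedule just before the count. What is missing is narrower: the kit is not named as the fallback when there is no day to count.

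**Stopping after the on-site first dose is not enough.** A reader might infer that every such woman has zero days. Intake is entered in the eDiary daily (Protocol 11.7), Month 6 diary data belong to the extension (SAP 5.2.1), and the next day's entry can fill a gap. She has no countable day only if those entries are missing too.

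**The data-loss routes may be partial.** Table 5, Case 2 concerns one vendor's device; Table 6 maps intake for the same case on the other. The language fault also concerns one device and some subjects. Protocol 10.3.1 provides alerts for missed entries and ongoing remote compliance checks. Either route matters only if it covers all of a woman's extension treatment, and nothing in the documents shows that this happened to anyone.

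**Reach.** A reader might infer that every safety table is affected. FU SAF requires entry to follow-up. Protocol 10.7.2 does not require the withdrawal DXA before Month 9, so early stoppers add little on-treatment BMD data. The placebo switchers serve a secondary objective (Protocol 13.5), and no hypothesis tests are planned.

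These points limit the size of the problem. They do not supply the missing rule.

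**Conclusion.** The gap is real and narrow. SAP 4.1 has no zero-day rule, and its tie rule applied as written gives a wrong label to one kind of subject: a placebo-to-75 mg switcher whose intake records are missing or excluded for her whole extension treatment, or who has no day with all three units recorded. Her adverse event, laboratory and other safety data, and BMD where collected, would appear under Placebo / LGX 200 mg + ABT in ESAF, and in FU SAF if she entered follow-up.

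The primary efficacy result, the continuing groups and the PK/PD analyses are untouched. The number of women is unknown and probably small. On the assumption of about 48 women per switch group, each one is about 2% of either group, and any error goes in the same direction. The conclusion rests on a literal reading of the tie rule. If the programmers already treat 0 versus 0 differently, the output may be right, but the SAP does not say so.

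**What to change.** In SAP 4.1, add that a subject with no qualifying eDiary day is assigned the regimen of the kits dispensed to her, from IWRS and accountability records, or the randomized regimen if that is unavailable. Limit the tie rule to equal counts above zero. It would also help to state that kit identity is what assigns a diary day to a regimen, and to list any subject classified by the fallback.

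This matches the SAP's practice elsewhere: compliance takes accountability first and the diary second (6.3.8.2), and the last treatment date takes the eCRF first and the diary second (5.2.1). The cost is a sentence or two and a small programming change. Kit numbers assigned to each subject are already recorded (Protocol 11.5).

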5.7 SUMMARY OF OVERALL RISKS AND BENEFITS

Linzagolix efficacy compared to placebo was demonstrated at daily doses of 75–200 mg for 3 months and maintenance of effect has been shown up to 6 months.

Linzagolix was well-tolerated at these doses. The most commonly reported AEs in the Phase 2 studies were headache and hot flush which are related to the biological activity of linzagolix.

Eleven pregnancies were in the Phase 2 studies. No fetal or newborn abnormalities were reported in any of the pregnancies.

There were no clinically relevant findings in laboratory measurements, vital signs or electrocardiogram (ECG) recordings. The administration of linzagolix results in infrequent, transient, moderate and non-dose-related increases in transaminase levels which were not associated with changes in bilirubin levels. A borderline increase in QTc interval was observed in healthy volunteers which was not considered clinically significant. Nevertheless, all subjects in the current study will be monitored monthly with ECG.

A modest degree of BMD loss has been seen in linzagolix-treated subjects with doses below 100 mg QD. Clinically significant BMD loss was observed with a dose of 200 mg QD at 6 months of treatment and requires combined use of hormonal ABT to mitigate BMD loss. As linzagolix 200mg will be combined with ABT in this extension study, no major impact on BMD is expected. In addition, the BMD loss will be monitored during the study and subjects who experience more than 8% confirmed BMD loss or a Z-score ≤ -2.5 will be discontinued from treatment. Moreover, subjects will be provided with vitamin D and calcium supplements which they will be recommended to take.

In addition, an independent Data Monitoring Committee (DMC) will oversee the safety of study subjects, including a regular review of transaminase levels, BMD values and ECG parameters.

In conclusion, linzagolix has a favorable benefit/risk ratio and represents a potential therapy for treating EAP.

The overall benefit/risk of this study was re-evaluated by ObsEva in light of the COVID-19 pandemic and evolving regulatory guidance.

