13.4 ANALYSIS SETS

The following data sets will be used for the statistical analysis:

1. **Treatment Extension Analysis Set:** All subjects from the main study who entered the extension study and received at least one dose of study drug with the exception of subjects whose Month 6 assessments subsequently met any of the discontinuation criteria listed in section 10.7.2.1. These subjects will be withdrawn from study treatment and will enter the Follow-Up Period. Subjects will be analyzed according to randomized treatment.
2. **Follow-up Extension Analysis Set:** All subjects from the main study who completed the 6 months of treatment in the extension study and who entered the Post-Treatment Follow-Up Period. Subjects will be analyzed according to randomized treatment.

3. **Extension Safety Analysis Set:** All subjects randomized into the extension study who received at least one dose of study drug irrespective of the treatment received. Subjects will be analyzed according to treatment received.
4. **Extension Pharmacokinetic (PK) Set:** all subjects who were randomized and received active study medication in the main study, had no major protocol deviations impacting PK throughout the main study or extension and with available PK data.
5. **Extension Pharmacodynamic (PD) Set:** all subjects who were randomized and received active study medication in the main study, had no major protocol deviations impacting PD throughout the main study or extension and with available PD data.

Individual data points may also be excluded from the analysis sets. Rules for such exclusions will be described in the statistical analysis plan (SAP).

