13.5 DATA ANALYSIS

The primary objective of this extension study is to assess the maintenance of efficacy of linzagolix administered orally once daily for up to an additional 6 months (for up to 12 months of treatment in total) in the subset of subjects who are treated with linzagolix up to the time point of interest. As such, the focus will be on subjects who received active treatment in the main study. The assessment of subjects who switched from placebo in the main study to active treatment in the extension study will be conducted as a secondary objective.

Subjects will be analyzed according to actual treatment received. The following four treatment groups will be analyzed: linzagolix 75 mg and linzagolix 200 mg with ABT fixed dose groups, linzagolix 75 mg and linzagolix 200 mg with ABT after 6 months placebo treatment. Only subjects with assessments at both baseline and the given time points will be included in the summaries. Baseline values are the same as in the main study (18-OBE2109-003 - Edelweiss 3), i.e. data collected prior to the treatment administration in the main study.

More details of the proposed statistical analyses will be described in the SAP, which will be written following finalization of the protocol and prior to database lock.

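### SAP 4.1 derives the extension treatment actually taken, then files all five off-plan sequences under a different extension label in safety tables meant to follow treatment received

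*SAP*

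**What the plan says.** SAP 4.1 defines the Extension Safety Analysis Set (ESAF) as "All subjects randomized into the extension study who received at least one dose of study drug irrespective of the treatment received", and has it analysed by the treatment received. The follow-up safety set and the PK and PD sets carry the same rule. It adds that "analyses of safety will be conducted using the ESAF and FU SAF". Protocol 13.4 says of the same safety set: "Subjects will be analyzed according to treatment received". Protocol 13.5 is broader: "Subjects will be analyzed according to actual treatment received".

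SAP 4.1 then gives the derivation from eDiary intake. The placebo rule opens "If a subject received placebo with placebo ABT on more than 50% of days (even if it is not planned", and such a woman is classed as placebo for the extension. Otherwise "the active treatment (combined with add-back or placebo add-back) with the most days taken will be assigned for the extension period". A tie between two active regimens goes to 200 mg + ABT.

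Next, SAP 4.1 states that all extension analyses use a group combining main-study and extension treatment, and tabulates nine combinations. Four are planned. The other five come under "Combination not planned in the protocol (but possible with treatment administration errors".

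SAP 6.2.1 defines the Placebo / linzagolix 75 mg group as women given placebo in the main study and treated with 75 mg in the extension. SAP 6.6.1 plans TEAE tables for the extension treatment period alone on the ESAF.

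**The concern.** The stated principle for safety and the mapping table disagree. The derivation finds which regimen a woman mainly took in the extension, and the table then sets that result aside for every sequence that was not planned.

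The extension has no concurrent control, so readers will judge safety by setting the dose columns side by side. An extension-period adverse event or laboratory value in a woman who mainly took 200 mg + ABT could stand in the 75 mg column, or the reverse. A woman classed as placebo in both studies would stand in a column that SAP 6.2.1 describes as treated with linzagolix. Nothing in the tables would show the reader that this had happened.

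**Working it through.** **Step 1. The plan's own sample size.** SAP 2.2: 450 × 0.80 = 360 completers, and 360 × 0.80 = 288 entrants. Both stated figures are reproduced. They serve only to scale Step 4.

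**Step 2. Compare each row of the SAP 4.1 table with the derived treatment.**

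| Main study | Extension, as derived | Filed as | Main part right? | Extension part right? |
|---|---|---|---|---|
| Placebo | 75 mg | Placebo / LGX 75 mg | yes | yes |
| Placebo | 200 mg + ABT | Placebo / LGX 200 mg + ABT | yes | yes |
| 75 mg | 75 mg | LGX 75 mg | yes | yes |
| 200 mg + ABT | 200 mg + ABT | LGX 200 mg + ABT | yes | yes |
| Placebo | Placebo | Placebo / LGX 75 mg | yes | **no** |
| 75 mg | Placebo | LGX 75 mg | yes | **no** |
| 200 mg + ABT | Placebo | LGX 200 mg + ABT | yes | **no** |
| 75 mg | 200 mg + ABT | LGX 75 mg | yes | **no** |
| 200 mg + ABT | 75 mg | LGX 200 mg + ABT | yes | **no** |

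The main-study part is right in 9 of 9 rows. The extension part is right in the 4 planned rows and wrong in all 5 off-plan rows.

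**Step 3. Collapse by main-study treatment.**
- Main 75 mg: all three extension results lead to one group, LGX 75 mg.
- Main 200 mg + ABT: all three lead to one group, LGX 200 mg + ABT.
- Main placebo: the result selects between two groups, and placebo defaults to Placebo / LGX 75 mg.

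So for a woman on active drug in the main study, neither the derivation nor the tie rule can change her column. The derivation has an effect only for ex-placebo women.

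**Step 4. Scale.** Assume the 288 entrants split equally across main-study arms, and the ex-placebo third splits 1:1 (Protocol 13.3). Each continuing-active column has 288 / 3 = 96 women, and each ex-placebo column 96 / 2 = 48.

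| Women misfiled | Share of n = 96 | Share of n = 48 |
|---|---|---|
| 1 | 1.04% | 2.08% |
| 2 | 2.08% | 4.17% |
| 5 | 5.21% | 10.42% |

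The documents give no count. These rows show a range, not an estimate.

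**Step 5. What triggers an off-plan row.** Linzagolix is dispensed as six monthly kits (Protocol 11.3) over 6 × 28 = 168 days. For a completer, a wrong-dose majority needs about four wrong kits (4/6 = 67% of days); three give a tie (3/6 = 50%). An early discontinuer needs fewer.

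**The case against.** The strongest defence is rarity. Kits are allocated automatically through the IWRS, several wrong kits are needed, and three of the five rows require placebo in the extension although neither regimen in Protocol 11.2 is all placebo. That stands, and it limits the size of the point.

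The second defence concerns tables spanning both studies, and BMD change from main-study baseline. There a woman who took 75 mg and then 200 mg + ABT has mixed exposure, no column fits, and a prespecified main-study label is a defensible convention. That also stands, but it does not carry over to extension-only tables.

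Third, the women remain traceable. Subject-linked deviations, exposure, compliance, and overdose or misuse are all listed (SAP 4.2, 6.3.8). However, none of these listings moves or flags a woman in a safety table. A switch from 75 mg to 200 mg is also not an overdose under Protocol 11.10, which sets the limit at 200 mg per day.

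Some stronger readings are tempting, but the documents do not support them:
- *Every wrong-dose woman is misfiled.* An ex-placebo woman who took the other active dose is filed by what she took.
- *The misattribution is total, or a placebo-classed woman took no linzagolix.* The rules work on a majority of days, so she may have taken the labelled dose on nearly half of them.
- *PK and PD results are equally exposed.* Both sets exclude major deviations affecting PK or PD, and both require active drug in the main study, so placebo/placebo women cannot enter. E2 is also reported under safety (SAP 6.6.3), so it is only partly protected.
- *The SAP foresees 200 mg without ABT and gives it no category.* Protocol 5.7 makes that exposure relevant ("Clinically significant BMD loss was observed with a dose of 200 mg QD at 6 months of treatment"), and linzagolix and ABT come in separate kits. But the add-back wording in the derivation also fits the two planned regimens, one with ABT and one with ABT placebo. One wrong ABT kit covers about 84 of 168 days, which is roughly a tie.

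**Conclusion.** The point holds as an internal contradiction in SAP 4.1. The safety sets are to follow treatment received, yet all five off-plan rows carry an extension label that is not the derived extension treatment. It matters most for extension-only safety tables on the ESAF, and no other section corrects it.

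The likely effect is small. The number of women is unknown and probably very small or zero. Under the equal-split assumption, each one is about 1 percentage point of a continuing-active column or about 2 points of an ex-placebo column. The efficacy sets are defined by randomized treatment and are unaffected, and no hypothesis test depends on the mapping. The correction is worth making because it is cheap and because readers will take the column labels at face value.

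**What to change.** In SAP 4.1:

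1. For safety tables restricted to the extension period on the ESAF, assign the column by the derived actual extension treatment, with a footnote where the main-study dose differed. Do the same in PK and PD summaries for any such woman not already excluded for a major deviation.
2. Show women classed as placebo in the extension separately, not in a linzagolix column.
3. For main-plus-extension tables and BMD change from main-study baseline, keep every dosed woman in the ESAF totals. Give the number of off-plan sequences, footnote them and list them by subject, including any linzagolix/ABT mix outside the two planned regimens. Removing these women would conflict with a set that includes everyone dosed.
4. Put tied-day cases in the same listing. The tie rule would move a continuing 75 mg woman to 200 mg + ABT in extension-only tables, and the reader should see that.
5. Leave the efficacy sets on randomized treatment.

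The cost is one derivation rule, one footnote and one listing. The drawback is that a few women may appear in different columns in extension-only and combined tables, which the footnote should explain.
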